### **9.6.3.3 Cough Visual Analog Scale**

Cough Visual Analogue Scale (VAS) scored from 0 to 100 using a 100 mm visual analogue scale will be evaluated at Screening, Baseline (Study Day -1), Days 28, 56, 84, Day 85/ETD, Follow-up (Day 112 and Day 113). Baseline cough VAS is defined as the cough VAS at Baseline (Study Day -1).

Change from baseline of cough VAS score will be analyzed in the same way as that for the primary endpoint as indicated in Section 9.6.2.1 above. To explore the correlation between VAS and 24-hour cough frequency, Scatter plots between VAS and 24-hour objective cough frequency counting will be generated.

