6.5.9 Day 85/Early Treatment Discontinuation Visit

The following procedures and evaluations will be performed at the clinic on Day 85 or within 7 days of the last dose of study drug for subjects who discontinue study drug treatment early.

At this visit, the following procedures and assessments are to be performed:

- Cough severity VAS
- PGIC
- LCQ
- Vital signs
- Weight
- Collect Day 84 cough monitor
- Complete physical exam
- ECG (12 lead)
- Laboratory tests
 - Reproductive endocrine labs for females under 55 years of age at time of consent
 - Endocrine
 - Hematology
 - Chemistry
 - Urinalysis
 - Urine pregnancy test for females of childbearing potential
 - Urine drug screen
- Contact IWRS to register Day 85 end of treatment visit
- Review IVRS/IWRS Days 57–84 dosing diary entries
- The following will be completed by the Investigator (MD or DO):

- CGIC
- Study drug - collect/performance accountability for Days 57–84 bottles (**early treatment discontinuation visit only**)
- Record all AEs
- Record all concomitant medication use
- Schedule Day 112 visit at clinic or at subject's home
- Schedule Day 113 visit at clinic

6.5.10 *Day 112 Follow-up Visit*

Subjects will return to the clinic or be visited by a mobile research nurse on Day 112 (± 3 days) for the following procedures and evaluations:

- Cough severity VAS
- Record all AEs
- Record all concomitant medication use
- Attach and activate cough monitor
 - Cough monitor will be collected the following day by a courier service and delivered to the clinic
- Contact IWRS to register the Day 112 Follow-up visit
- Remind subject about Day 113 visit at clinic

6.5.11 *Day 113 Follow-up Visit*

Subjects will return to the clinic on Day 113 for the following procedures and evaluations:

- Vital signs
- Collect Day 112 cough monitor
- Cough severity VAS
- LCQ
- Contact IWRS to register the Day 113 Follow-up visit
- Complete physical exam
- ECG (12-lead)

- Laboratory tests
 - Reproductive endocrine labs for females under 55 years of age at time of consent
 - Endocrine
 - Hematology
 - Chemistry
 - Urinalysis
 - Urine pregnancy test for females of childbearing potential
 - Urine drug screen
- Record all AEs
- Record all concomitant medication use

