APPENDIX A (CONT'D)

Table 4 Schedule of Cough Monitoring and Patient Reported Outcomes (PROs)

Cough monitoring devices (VitaloJAK) will be stored at each study center and attached to subjects at the visits shown below. The PROs will be completed within IVRS/IWRS or on paper as shown below. PROs are provided to subjects at the screening visit.

Device	Assessment	Frequency and Duration of Assessment
VitaloJAK	Cough Monitoring	Baseline, Day 28, Day 56, Day 84, Day 112
IVRS/IWRS	Daily dosing	Daily during the 84-day treatment period
Paper	Cough Severity VAS	Once at Screening, Baseline, Day 28, Day 56, Day 84, Day 85, Day 112, Day 113
Paper	LCQ	Baseline, Day 28, Day 56, Day 84, Day 113
Paper	PGIC	Day 28, Day 56, Day 84

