## 8.2 Determination of Sample Size

The comparisons related to the primary and key secondary endpoints will be done in a hierarchical manner to control the familywise error rate. The testing procedure will start by testing the primary endpoint and then proceed to the key secondary endpoints by following the order as specified in Section 8.9.4.

A total of 170 subjects (85/arm) in 1:1 ratio to serlopitant 5 mg or placebo will provide 90% power to detect a 25% relative reduction (placebo-adjusted ratio of 0.75) in 24-hour objective cough frequency or awake objective cough frequency using a two-sample t-test at a one-sided significance level of 0.05. This assumes that 24-hour cough frequency or awake cough frequency follows a log-normal distribution with a CV of 0.64. This sample size also considers an expected dropout rate of 15%.

The sample size calculations have been performed in nQuery Advisor + nTerim.

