## 8.5 Adjustments for Covariates

The primary endpoint will be evaluated using a mixed effect repeated measures (MMRM) model which includes fixed effects for treatment group, visit, country, sex, the treatment-by-visit interaction, and the baseline value as a covariate. In addition, exploratory analysis of the primary endpoint will be conducted by adjusting additional covariates such as age and duration of cough in the MMRM model.

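### The H5 VAS model adjusts for one baseline score and leaves the pre-dose Screening VAS, collected on every eligible subject, out of the analysis

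*SAP*

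**What the plan says.** SAP 8.7 places change in cough severity VAS at Week 12 (Day 84) fifth in the sequence, tested at one-sided 0.05. Protocol 3.3.2 and SAP 5.1.2 name the same visit.

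Protocol Appendix A, Table 4 gives the VAS schedule: "Once at Screening, Baseline, Day 28, Day 56, Day 84, Day 85, Day 112, Day 113". Protocol 4.2 requires at least 40 mm at both Screening and Baseline. Two pre-dose scores should therefore exist for each eligible subject.

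For analysis, SAP 9.6.3.3 keeps one of them: "Baseline cough VAS is defined as the cough VAS at Baseline (Study Day -1"). The protocol calls this visit Day 0 and the SAP calls it Study Day -1; SAP Appendix C shows that they are the same visit. The section then refers VAS to the primary-endpoint methods in 9.6.2.1. SAP 8.5 describes that model as fixed effects for treatment, visit, country and sex, plus "the treatment-by-visit interaction, and the baseline value as a covariate". Neither document gives the Screening VAS any use beyond eligibility.

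**The concern.** A single-item scale read once carries visit-to-visit error, and error in the baseline covariate limits how much between-subject variation the model can remove. A second pre-dose reading of the same scale is the obvious extra covariate. It predates randomization, should be complete, and has already been collected. Leaving it out does not make the H5 test wrong. It makes the standard error somewhat larger than it need be for an alpha-controlled endpoint on which the trial was not sized.

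**Working it through.** **1. The plan's own figure.** The documents size the trial on cough frequency only.
- Inputs, all from SAP 8.2: "will provide 90% power to detect a 25% relative reduction (placebo-adjusted ratio of 0.75"), "using a two-sample t-test at a one-sided significance level of 0.05", "follows a log-normal distribution with a CV of 0.64", and 15% dropout.
- Log-scale SD = sqrt(ln(1 + 0.64²)) = 0.586. Effect = ln(0.75) = -0.288.
- The two-sample formula gives 72 per arm (exact t-test power 0.901). 72/0.85 = 84.7, so 85 per arm and 170 in total.
- This matches "A total of 170 subjects (85/arm) in 1:1 ratio to serlopitant 5 mg or placebo". No power, SD, effect or correlation is given for VAS, so everything below rests on assumed values.

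**2. Correlation-based calculation.** With complete data, the Day 84 contrast from an unstructured MMRM is close to an ANCOVA at Day 84. Let ρ be the correlation of each pre-dose score with the Day 84 score, and r the correlation between Screening and Baseline. Assume equal variances.
- Baseline score only: residual variance ∝ 1 - ρ².
- Both scores as covariates: residual variance ∝ 1 - ρ²/((1 + r)/2).

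With ρ = 0.5 the first is 0.75:

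| r | Both scores | Ratio to 0.75 | Reduction |
|---|---|---|---|
| 0.9 | 0.737 | 0.98 | 2% |
| 0.8 | 0.722 | 0.96 | 4% |
| 0.7 | 0.706 | 0.94 | 6% |
| 0.6 | 0.688 | 0.92 | 8% |

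With ρ = 0.3 the ratios are closer to 1: 0.995 at r = 0.9 and 0.983 at r = 0.7.

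At the favourable end, 72 evaluable subjects per arm would act like 72/0.917, or about 79. At the other end they would act like 72/0.983, or about 73. A test with 80% power would move to about 83% or 81% respectively.

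**3. Simulation with the entry threshold.** True score = mean 60 or 65 mm plus a between-subject deviation (SD 12, 15 or 18). Each reading adds independent within-visit error (SD 6, 10 or 15). The true change has SD 12. Only subjects with both entry scores at or above 40 mm are kept. The residual variance of the Day 84 score on Baseline plus Screening, divided by that on Baseline alone, runs from 0.91 to 0.96 over these settings. That is a reduction of about 4-9%.

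**4. When Screening is a poorer predictor.** Suppose Screening correlates 0.3 with Day 84, Baseline correlates 0.5, and the two correlate 0.6.
- Averaging the two scores: correlation with Day 84 = 0.4/sqrt(0.8) = 0.447, so the residual is 1 - 0.20 = 0.80. Against 0.75 the ratio is 1.07, a loss.
- Entering both as covariates: R² = (0.09 + 0.25 - 2 × 0.3 × 0.5 × 0.6)/(1 - 0.36) = 0.16/0.64 = 0.25. This equals the Baseline-only value, so nothing is gained and nothing is lost apart from one degree of freedom.

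The second score should therefore enter as a covariate and should not be averaged into the baseline.

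**The case against.** **One baseline and one target visit is a legitimate choice.** The sections cited agree with one another on the VAS baseline and the Day 84 endpoint. This stands: the point concerns efficiency, and the H5 test as planned is valid.

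**Screening is not a clean replicate.** It carries the same 40 mm threshold, can fall 14 days or more before Baseline, and can precede the opioid washout, which starts one week before Baseline (Protocol 5.7.2). This also stands. It is why the gain may be small, and why a covariate is preferable to an average.

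**The consequence is small.** H5 is reached only if H1 to H4 all succeed. This stands too.

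**A reader might go further and infer that Day 84 and Day 85 VAS should be averaged as well.** Protocol 6.5.9 does list "Cough severity VAS" at the Day 85 visit. However, the endpoint is fixed at Day 84 in both documents, so averaging would redefine an alpha-controlled endpoint. The same visit also serves early discontinuers, up to 7 days after the last dose. With the half-life of 45-86 hours in Protocol 1.3.1, 0.5^(24/45) to 0.5^(24/86), or 69-82% of drug, remains after one day. After seven days only 0.5^(168/45) to 0.5^(168/86), or 8-26%, remains. Mixing such scores in would change what H5 measures. A subject who misses only Day 84 is not lost either, because the MMRM keeps that subject's Day 28 and Day 56 data under missing at random.

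**A reader might also infer that the unused scores are worth 15-40% more subjects.** That figure needs the Day 84/85 average, and its upper end needs uncorrelated errors on adjacent days. If those errors correlate 0.9, averaging saves only about 1-2%. The documents contain nothing that supports the larger figure.

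**Conclusion.** The point holds as a minor efficiency suggestion. The H5 model omits a pre-dose covariate that is available on every eligible subject. Adding it cannot bias the comparison, and under the assumed values it cuts Week 12 residual variance by about 4-9% (simulation) or 2-8% (correlation-based, ρ = 0.5, r from 0.6 to 0.9). The reduction shrinks to 2% or less at ρ = 0.3 with r of 0.7 or more. It vanishes if Screening tells nothing about Week 12 beyond what the Baseline visit does. None of these variances or correlations comes from the documents. The documents do not support reading this as a flaw in the validity of H5.

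**What to change.** In SAP 9.6.3.3, before unblinding, add Screening VAS as a second baseline covariate in the H5 MMRM. Keep the Baseline-visit score as the baseline for change and Day 84 as the endpoint visit.

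State that Screening VAS enters on the same scale as the existing covariate. The wording should say which scale that is, since 9.6.2.1 contains both a log-scale and an original-scale model and 9.6.3.3 does not choose between them.

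The cost is one model parameter and a sentence or two of SAP text. No new data, visit or change to the endpoint definition is needed. Protocol 8.9.3 says that continuous secondary endpoints use the primary MMRM, so the SAP should record the added covariate as a deliberate departure for VAS.

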### **9.6.4 Other Secondary Endpoints**

The following secondary endpoints are planned for analysis:

#### **9.6.4.1 Sleep Objective Cough Frequency**

Analyses for sleep objective cough frequency will proceed in the same manner as the analyses indicated in Section 9.6.2.2 above at for the Primary Efficacy endpoint.

#### **9.6.4.2 Cough Frequency at Follow-Up**

In order to assess whether 12 weeks of treatment with serlopitant can delay the return of chronic cough, the observed results, change from Day 84, and change from baseline for 24-hour cough frequency, awake cough frequency, and sleep cough frequency at Follow-up Visit (Day 112) will be also summarized.

#### **9.6.4.3 Leicester Cough Questionnaire (LCQ)**

The Leicester cough questionnaire (LCQ) instrument will be assessed at Baseline (Study Day0), Day 28, Day 56, 85/Early Termination, and Follow-up (Day 113). There are three domains in the LCQ instrument: Physical (items 1, 2, 3, 9, 10, 11, 14 and 15), Psychological (4, 5, 6, 12, 13, 16, and 17), and Social (7, 8, 18, 19). For each domain, the domain score (range 1-7) is the sum of individual item score within the domain divided by the number of items in the domain; total LCQ score (range 3-21) is the sum of the three domain scores. Baseline LCQ is defined as the LCQ collected at Baseline (Study Day -1).

For each domain (physical, psychological, and social) and total LCQ score, change from baseline will be analyzed in similar manner as indicated for the primary endpoint in Section 9.6.2.1. Line plots of individual subject baseline and post treatment scores will be generated by treatment group and serlopitant for each domain and total LCQ scores.

#### **9.6.4.4 Patient's Global Impression of Change**

The self-report measure Patient's Global Impression of Change (PGIC) reflects a patient's belief about the efficacy of treatment. PGIC is a 7-point scale depicting a patient's rating of overall improvement. Patients rate their change as "very much improved," "much improved," "minimally improved," "no change," "minimally worse," "much worse," or "very much worse." The counts and proportions of ordered responses to the subject's global perception of change will be computed for each treatment group on Day 28, Day 56, Day 85/ETD. Proportion of subjects with improvements (either "very much improved" or "much improved" on the PGIC scale) will also be presented. The distribution of responses will be compared between each of the serlopitant treatment groups and placebo using the stratified Cochran Mantel Haenszel (CMH) test (stratified by country and sex, unless stated otherwise).

#### **9.6.4.5 Clinician's Global Impression of Change**

The Clinician's Global Impression of Change (CGIC) reflects a clinician's belief about the efficacy of treatment. CGIC has the same 7-point scale like PGIC.

CGIC will be evaluated at Day 85/ETD. Similar analysis for PGIC will be applied for CGIC.

#### **9.6.5 Sensitivity Analysis**

The primary analyses (MMRM) for assessing 24-hr cough frequency and awake cough frequency are valid if the missing data are missing at random (MAR), meaning that the probability of a value being missing, conditional on the observed data and factors in the statistical model, is random and not dependent on the unknown value of the missing data point. Therefore, two sensitivity analyses under missingness not at random (MNAR) will be conducted for 24-hr cough frequency and awake cough frequency to evaluate the robustness of efficacy results and the effect of missing data.

Sensitivity analysis using a copy-reference multiple-imputation method will be performed to assess the robustness of the primary analysis based on MMRM. In this sensitivity analysis, intermittent missing values will be imputed using the Markov Chain Monte Carlo (MCMC) methodology which assumes a multivariate normal distribution over all variables included in the imputation model. This imputation will be done by treatment group, using MI procedure in SAS 9.4. The variables to be used in the imputation are treatment, corresponding baseline values, and values observed at all double-blind visits (Days 28, 56, and 84). Then all the monotone missing values will be multiply-imputed using the imputation model built from the control group, i.e., assuming the missing data in the treatment group will have a profile that equals the profile of the control group for all time points (i.e., a copy-reference imputation). The missing data imputation will be implemented using PROC MI in SAS 9.4 with the MNAR statement. Once the competed

data sets are formed, the same MMRM analysis model as specified for the primary analysis will be applied to each completed set and the inference drawn using Rubin's combination rules (SAS proc MIANALYZE). While the results will be combined using SAS PROC MIANALYZE, it is known that this approach may produce an inflated variance estimate for the treatment comparison. To get a correct variance, a pattern mixture model approximation method will also be used. Results from both the MIANALYZE and the pattern mixture model approximation will be presented as sensitivity analyses. A sample of SAS code for sensitivity analysis using the copy-reference MI method is provided in Appendix A.

An additional sensitivity analysis using the tipping-point approach will be conducted to assess the robustness of the primary analysis approach. If it is plausible that, for the active treatment group, the distribution of missing primary endpoint responses has a smaller expected reduction than that of the corresponding distribution of the observed primary endpoint responses, the conclusion under the MAR assumption should be examined. It is desired to impose a fixed and definite set of quantities to encapsulate the change in efficacy associated with withdrawal (missing) for the active treatment group, and the tipping point multiple imputation analysis as described in Ratitch et al. (2013) will be applied. Tipping point analysis is a means of exploring the influence of missingness on the overall conclusion from statistical inference by positing a wide spectrum of assumptions regarding the missingness mechanism (from less conservative to more conservative). The analysis finds a (tipping) point in this spectrum of assumptions, at which conclusions change from being favorable to the experimental treatment to being unfavorable. After such a tipping point is determined, clinical judgment can be applied as to the plausibility of the assumptions underlying this tipping point. The tipping point can be identified while the result is no longer statistically significant. This imputation analysis used a specified sequence of shift parameters, which adjust the imputed values for observations in the active treatment group. The tipping point can be identified while the result is no longer statistically significant. A sample of SAS code for sensitivity analysis using the tipping-point method is provided in Appendix A.

For both sensitivity analyses, the multiple imputations will be completed before log-transforming data.

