### 9.6.2.1 Analyses of Primary Endpoint

#### A. Primary Analysis - Mixed Model Repeated Measures Analysis of Log Transformed 24-hour Cough Frequency:

As the change in 24-hour cough frequency may have a skewed and wide distribution, the primary analysis for the primary endpoint will be on the natural log scale of the cough frequency data. The difference between serlopitant 5 mg and placebo will be estimated using a mixed effect repeated measures (MMRM) model. The model will include fixed effects for treatment group, visit, country, sex, the treatment-by-visit interaction, and the log-transformed baseline value as a covariate. The MMRM model will use all available 24-hour cough frequency data on Day 28, 56, and 84. An unstructured covariance structure will be applied for MMRM. In case the model will not converge with the unstructured covariance structure, the heterogeneous compound symmetry (CSH) will be used instead. Furthermore, if the model fails to converge with CSH, the heterogeneous Toeplitz structure (TOEPH) will be used. If the unstructured covariance structure will be used, the denominator degrees of freedom will be computed using the Kenward-Roger method. In case of other covariance structures, the BETWITHIN (SAS®) option will be used for the denominator degrees of freedom. Contrasts will be constructed to compare each of the three serlopitant treatment groups to the placebo group at each visit. The least-squares (LS) mean change from baseline (on the log scale) with the associated standard errors will be displayed for each treatment group. Estimated treatment differences (serlopitant vs. placebo) along with corresponding one-sided 95% CIs and p-values will also be presented at each post-baseline timepoint.

In addition, the geometric mean of 24-hour cough frequency will be presented by treatment and by visit. The percent difference change between serlopitant and placebo will be estimated by  $100(e^{\text{diff}} - 1)$ , where diff is the difference provided by the analysis of the log-transformed variable. A sample of SAS code for MMRM analysis is provided in Appendix A.

An observation of zero coughs per hour will be replaced by a cough rate of 0.1 for the calculation of geometric means.

Missing data, in the assessment of the primary hypothesis, is assumed as missing at random (MAR). This assumption will be assessed with a missing data sensitivity analysis (see Section 9.6.5 Sensitivity analysis of the primary endpoint).

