**A sample of the SAS code for sensitivity analysis using the copy-reference MI method is provided as below:**

```
/*Generate transpose of adcf - wide format before Step 1*/
/*----- Generates 10 imputed data sets based on original (non-transformed)
data-----*/
/*Step 1: Achieve Monotone Missing Data Pattern */
PROC MI DATA=&DATA SEED=14823 NIMPUTE=10 OUT=MONO;
  /* Use numeric TRT01PN */
  VAR BASE AVAL1 AVAL2 AVAL3; /*Refer to AVAL at Visits 5, 6, and 7*/
  MCMC IMPUTE=MONOTONE NBITER=5000 NITER =5000;
  BY TRT01PN;
run;

/*Step 2: Achieve Control-Based Copy-Reference Imputation */

PROC MI DATA=MONO SEED=14823 NIMPUTE=1 OUT=OUTM1;
  CLASS TRT01PN;
  By _IMPUTATION_;
  VAR TRT01PN BASE AVAL1 AVAL2 AVAL3;
  MONOTONE REG (AVAL2 AVAL3);
  MNAR MODEL (AVAL1 AVAL2 AVAL3/ MODELOBS = (TRT01PN = '0'));
  /*Control=Placebo*/
RUN;
PROC SORT DATA =OUTM1; BY _IMPUTATION_ TRT01PN USUBJID LBASE; RUN;
/*Generate transpose of OUTM1 - skinny format before Step 3*/

/*Step 3: Run MMRM Analysis on Imputed Data */

PROC MIXED DATA=OUTM1 METHOD=REML;
  BY _IMPUTATION_;
  CLASS TRT01PN USUBJID AVISITN COUNTRY SEX;
```

```

MODEL LCHG = TRT01PN AVISITN COUNTRY SEX TRT01PN*AVISITN LBASE / DDFM=KR;
/*LCHG AND LBASE ARE BASED ON THE LOG-TRANSFORMED COUGH FREQUENCY*/
REPEATED / SUBJECT=USUBJID (TRT01PN) TYPE=UN;
LSMEANS TRT01PN*AVISITN / CL DIFF PDIFF;
  ESTIMATE 'TRT S - P ON DAY 28' TRT01PN -1 1
            TRT01PN*AVISITN -1 0 0 1 / CL LOWER LOWERTAILED;
  ESTIMATE 'TRT S - P ON DAY 56' TRT01PN -1 1
            TRT01PN*AVISITN 0 -1 0 0 1 / CL LOWER LOWERTAILED;
  ESTIMATE 'TRT S - P ON DAY 84' TRT01PN -1 1
            TRT01PN*AVISITN 0 0 -1 0 0 1 / CL LOWER LOWERTAILED;
ODS OUTPUT PARAMETERESTIMATES=PESTIMATES;
RUN;
```

```

/*Step 4: Combining estimates from each imputed data set */
/*First, sort the data of estimates by visit (variable "LABEL") */
PROC MIANALYZE DATA=PESTIMATES;
  MODELEFFECTS ESTIMATE;
  STDERR STDERR;
  BY LABEL;
  ODS OUTPUT PARAMETERESTIMATES= MIPARM;
RUN;
```

A sample of the SAS code for sensitivity analysis using the tipping-point approach is provided as below:

```

/*-----*/
/*--- Performs multiple imputation analysis ---*/
/*--- for specified shift parameters: ---*/
/*--- data= input data set ---*/
/*--- smin= min shift parameter ---*/
/*--- smax= max shift parameter ---*/
/*--- sinc= increment of the shift parameter ---*/
/*--- outparms= output parameters ---*/
/*-----*/

%MACRO MIPARMS( DATA=, SMIN=, SMAX=, SINC=, OUTPARMS=);

DATA &OUTPARMS;

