  SET _NULL_;
RUN;

/*----- # of shift values -----*/
%LET NCASE= %SYSEVALF( (&SMAX-&SMIN)/&SINC, CEIL );

/*---- Multiple imputation analysis for each shift ----*/
%DO JC=0 %TO &NCASE;
  %LET SJ= %SYSEVALF( &SMIN + &JC * &SINC);

  /*---- Generates 10 imputed data sets ----*/
```

```
/*Step 1: Achieve Monotone Missing Data Pattern */
PROC MI DATA=&DATA SEED=14823 NIMPUTE=10 OUT=MONO;
  ** Use numeric TRT01PN ;
  VAR BASE AVAL1 AVAL2 AVAL3; /*Refer to AVAL at Visits 5, 6, and 7*/
  MCMC IMPUTE=MONOTONE NBITER=5000 NITER =5000;
  BY TRT01PN;
run;

/*Step 2: Impute all visits under MAR first, then apply delta adjustments at
each visit*/
PROC MI DATA=OUTM1 SEED=14823 NIMPUTE=1 OUT=OUTM2;
  CLASS TRT01PN;
  BY _IMPUTATION_;
  VAR TRT01PN BASE AVAL1 AVAL2 AVAL3;
  MONOTONE REG (AVAL2 AVAL3);
  MNAR ADJUST( AVAL1 / SHIFT=&SJ ADJUSTOBS=(TRT01PN ='1') );
  MNAR ADJUST( AVAL2 / SHIFT=&SJ ADJUSTOBS=(TRT01PN ='1') );
  MNAR ADJUST( AVAL3 / SHIFT=&SJ ADJUSTOBS=(TRT01PN ='1') );
  RUN;
  PROC SORT DATA =OUTM1; BY _IMPUTATION_ TRT01PN USUBJID BASE; RUN;
/*Generate transpose of OUTM2 - skinny format before Step 3*/

/*Step 3: Run MMRM Analysis on Imputed Data */

PROC MIXED DATA=OUTM2 METHOD=REML;
  BY _IMPUTATION_;
  CLASS TRT01PN USUBJID AVISITN COUNTRY SEX;
  MODEL LCHG = TRT01PN AVISITN COUNTRY SEX TRT01PN*AVISITN LBASE /
  DDFM=KR; /*CHG AND BASE ARE BASED ON THE LOG-TRANSFORMED COUGH
FREQUENCY*/
  REPEATED / SUBJECT=USUBJID (TRT01PN) TYPE=UN;
  LSMEANS TRT01PN*AVISITN / CL DIFF PDIFF;
  ESTIMATE 'TRT S - P ON DAY 28' TRT01PN -1 1
           TRT01PN*AVISITN -1 0 0 1 / CL LOWER LOWERTAILED;
  ESTIMATE 'TRT S - P ON DAY 56' TRT01PN -1 1
           TRT01PN*AVISITN 0 -1 0 0 1 / CL LOWER LOWERTAILED;
  ESTIMATE 'TRT S - P ON DAY 84' TRT01PN -1 1
           TRT01PN*AVISITN 0 0 -1 0 0 1 / CL LOWER LOWERTAILED;
  ODS OUTPUT PARAMETERESTIMATES=PESTIMATES;
  RUN;
/*First, sort the data of estimates by visit (variable "LABEL") */
PROC SORT DATA=PESTIMATES; BY LABEL; RUN;

/*Step 4: Combining estimates from each imputed data set */
PROC MIANALYZE DATA=PESTIMATES;
  MODELEFFECTS ESTIMATE;
  STDERR STDERR;
  BY LABEL;
  ODS OUTPUT PARAMETERESTIMATES=MIPARM;
```

```
RUN;

DATA MIPARM;
  SET MIPARM;
  SHIFT= &SJ;
RUN;

/*----- Output multiple imputation results -----*/
DATA &OUTPARMS;
  SET &OUTPARMS MIPARM;
RUN;

%END;
%MEND MIPARMS;

/*Assume that the tipping point for the shift parameter that reverses the
study conclusion is between 0 and 100. The following statement performs

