multiple imputation analysis for each of the shift parameters 0,10,20,30,...,
100.*/

ODS LISTING CLOSE;
%MIPARMS (DATA=XXXX, SMIN=0, SMAX=100, SINC=10, OUTPARMS=PARMS1);

/* Step 5: Finding Tipping Point for Shift Parameter between 0 and 100 such
that p-value is less than 0.05, below is an example for a tipping point for
the shift parameter between 40 and 50.

For a two-sided Type I error level of 0.05, the tipping point for the shift
parameter is greater than 40. The following statement performs multiple
imputation analysis for shift parameters 40, 41, ..., 50*/

%MIPARMS (DATA=XXXX, SMIN=40, SMAX=50, SINC=1, OUTPARMS=PARM2);

/*The following statements display the p-values that are associated with the
shift parameters.*/

PROC PRINT LABEL DATA=PARM2;
  VAR SHIFT PROBT;
  TITLE 'P-VALUES FOR SHIFT PARAMETERS';
  LABEL PROBT='PR > |T|';
  FORMAT PROBT 8.4;
RUN;
```

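### Both missing-data sensitivity analyses impute cough rates on the original scale and take logs afterwards, with no rule for zero or negative draws; this inflates the copy-reference standard error

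*SAP*

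**What the plan says.** - **Order of steps.** SAP 9.6.5: "For both sensitivity analyses, the multiple imputations will be completed before log-transforming data".
- **Imputation model.** For intermittent gaps, SAP 9.6.5 uses MCMC, "which assumes a multivariate normal distribution over all variables included in the imputation model". Monotone gaps are then filled by a regression model built from the control group.
- **Sample code, copy-reference (Appendix A).** The comment reads "Generates 10 imputed data sets based on original (non-transformed", cut here before its last word. The MCMC and MONOTONE REG statements carry no minimum and no transform. The MMRM is then run on log change with log baseline.
- **Sample code, tipping-point (Appendix A).** Same structure: "Impute all visits under MAR first, then apply delta adjustments". The shifts are in coughs per hour, with grid "SMIN=0, SMAX=100, SINC=10".
- **Distribution.** SAP 8.2 assumes that cough frequency "follows a log-normal distribution with a CV of 0.64", and SAP 9.6.2.1 A makes the log-scale MMRM primary.
- **Zeros.** The only rule is in SAP 9.6.2.1 A: "An observation of zero coughs per hour will be replaced by a cough rate of 0.1 for the calculation of geometric means".
- **Variance.** SAP 9.6.5 warns that the MIANALYZE route can overstate the variance, and adds: "To get a correct variance, a pattern mixture model approximation method will also be used". Both results are to be reported.

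**The concern.** The imputation model contradicts the SAP's own view of the data. A normal model for a right-skewed, strictly positive rate puts probability below zero, and those draws have no logarithm. The zero rule does not reach them: it concerns an observed zero, in the calculation of geometric means. The programmer must drop, floor or redraw them, and the answer depends on which.

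A rule for non-positive draws would still not be enough. At an assumed median of 20 coughs per hour and a log SD of 0.586, a draw of 0.5 per hour lies ln(0.5/20)/0.586 = -6.3 SDs from the median on the log scale. Such values widen the spread within and between imputed data sets for reasons unrelated to missing-data uncertainty.

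At stake is how the robustness analysis is read. Section 9.6.5 exists to show whether the primary result survives other missing-data assumptions. An inflated standard error can make a sound result look fragile.

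**Working it through.** **The plan's own figure first.** Log SD = sqrt(ln(1 + 0.64²)) = 0.586; effect = ln(0.75) = -0.288. A two-sample t-test at one-sided 0.05 needs 72 evaluable per arm (power 0.901). 72/0.85 = 84.7, so 85 per arm and 170 in total. SAP 8.2 reproduces.

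**Rough size of the problem.** A normal variable with CV 0.64 falls at or below zero with probability Φ(-1/0.64) = 5.9%.

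**Simulation inputs.** From SAP 8.2: CV 0.64, 85 per arm, ratio 0.75, 15% dropout. Assumed, because the documents give no value:
- within-subject log correlation 0.5, 0.7 or 0.85, exchangeable, with equal variance and the same ratio at every post-baseline visit;
- monotone dropout, completely at random.

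The imputed share is also not given. The FAS (SAP 6.1) removes subjects with no on-treatment recording after baseline, so 15% is an upper case. Three cases were run:
- (a) 7.5% missing by Day 56 and 15% by Day 84;
- (b) half of that;
- (c) half of the dropouts leave before the Day 28 recording, so the FAS is 85 × 0.925 ≈ 79 per arm and 7.5/92.5 ≈ 8% of Day 84 values are imputed.

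**Method.** Each trial had 10 imputations by sequential Bayesian regression fitted in placebo, on the original or the log scale. Day 84 was analysed by ANCOVA on log baseline and combined by Rubin's rules, with 600 trials per setting. Country, sex and intermittent gaps were omitted. Placebo was the reference arm, as the 9.6.5 text intends; the treatment codes in the sample code do not match Appendix A's own key, which is a separate matter.

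**Copy-reference, original-scale v log-scale imputation** (non-positive draws dropped unless stated; ratio 0.75 unless stated; percentages from unrounded SEs):

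| | r = 0.5 | r = 0.7 | r = 0.85 |
|---|---|---|---|
| Imputed values ≤ 0, (a) | 6.1% | 4.7% | 2.8% |
| Per data set (× 25.5 imputed) | 1.6 | 1.2 | 0.7 |
| SE, (a) | 0.097 v 0.085 | 0.082 v 0.069 | 0.065 v 0.051 |
| SE increase, (a) | 13% | 19% | 26% |
| SE increase, (b) | 8% | 10% | 15% |
| SE increase, (c) | 8% | 11% | 16% |
| Redrawn until positive, (a) | 14% | 20% | 28% |
| Redrawn until positive, (c) | 8% | 12% | 16% |
| Set to 0.1, (a), median 20/h | 64% | 69% | 72% |
| Significance lost, ratio 0.75, (a) | 3.5% | 1.7% | 0.0% |
| Significance lost, ratio 0.75, (c) | 1.8% | 1.2% | 0.0% |
| Significance lost, assumed ratio 0.85, (a) | 11% | 15% | 9% |
| Significance lost, assumed ratio 0.85, (c) | 5% | 8% | 6% |

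Significance lost means one-sided p < 0.05 with log-scale imputation but not with original-scale imputation. The reverse occurs in 1.2% of trials or fewer. With draws dropped, estimates in (a) differ by 0.002 or less. Setting draws to 0.1 over assumed medians of 10 to 100 per hour gives +53% to +101% in (a) and +34% to +64% in (c), with the estimate up to about 0.01 more favourable to active.

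**Checks.** A three-visit unstructured MMRM in place of ANCOVA gave SE ratios of 1.143, 1.195 and 1.265 in (a) and 1.086, 1.095 and 1.150 in (c). A second simulation at correlation 0.6 with 15% imputed gave mean SEs of 0.091 v 0.078, while the empirical SD of the estimate was 0.070 v 0.072. The extra SE is therefore not real sampling variability.

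**Tipping-point** (15% imputed, median 20/h, ratio 0.75, draws dropped; the log-scale comparator adds the same coughs-per-hour shift after back-transforming). The SE increase is 14 / 19 / 27% at shift 0, 10 / 12 / 13% at shift 10 and 5 / 6 / 6% at shift 30. The median tipping point is 30 / 30 / 30 v 30 / 30 / 40 coughs per hour. It comes earlier with original-scale imputation in 18 / 24 / 24% of trials and later in 17 / 8 / 5%. At shift 10 the estimate moves slightly towards active (for example -0.215 v -0.203 at correlation 0.5).

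**The case against.** The best defence is that the SAP already flags this standard error as inflated and reports a second result meant to correct it. That stands in part, since a reader is warned. But the warning is about the MIANALYZE route in general and does not mention scale. The log-scale comparator above uses the same combination rules, so the inflation shown is additional. The documents give no formula for the pattern mixture approximation, so whether it escapes the problem cannot be computed.

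Decision impact is small, and this stands. No pass/fail rule hangs on 9.6.5, the estimate barely moves when draws are dropped, and at the design ratio of 0.75 significance is lost in at most 3.5% of trials. The larger losses need a ratio of 0.85, which is not in the documents.

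The size rests on assumptions. This also stands: correlation, dropout pattern and median rate are not in the documents, and case (c) fits the FAS definition better than case (a). The 0.1 figures show one possible programming choice, not the plan. The code is labelled a sample, so its missing bounds and its grid are weaker evidence than the 9.6.5 sentence, which carries the point alone.

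Finally, shifts in coughs per hour are a reasonable unit for clinical judgement. The fix allows them to be kept.

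**Conclusion.** The concern holds and is minor. The stated order of imputing and logging conflicts with the SAP's log-normal assumption and leaves an unstated programming choice that changes the result. The demonstrated harm is to the copy-reference MIANALYZE standard error: about 8 to 16% too large when 8% of Day 84 values are imputed, and 13 to 26% in the upper case of 15%, if non-positive draws are dropped. Redrawing them does no better, and borrowing the 0.1 rule is much worse. With draws dropped the error is conservative.

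For the tipping-point analysis the effect is small near the shifts at which significance is usually lost, and it has no consistent direction. Confidence in the direction of the copy-reference effect is high, since the SE rose in every setting run. Confidence in its size is moderate, because it depends on the assumed correlation, dropout pattern and imputed share.

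**What to change.** - Reverse the sentence in SAP 9.6.5, so that baseline and post-baseline cough frequencies are log-transformed before both PROC MI steps and log change is analysed directly.
- Widen the zero rule in SAP 9.6.2.1 so that an observed zero is set to 0.1 before that transformation. Whether the primary MMRM treats an observed zero the same way is a separate gap. It should be settled at the same time, so that the analyses stay comparable.
- For tipping-point, restate the shift grid on the log (ratio) scale. If shifts in coughs per hour are preferred, add them after back-transforming the log-scale imputations, then take logs again.
- Amend the PROC MI code and the 0 to 100 grid in Appendix A to match.

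The cost is SAP text and code edits before database lock, with none in data or patients. Protocol 8.9.2.1 names no imputation scale and leaves technical detail to the SAP, so changing the imputation scale needs no protocol amendment.
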